8.3 Definitions of Screening Test Results

The result of either screening exam (DBT or MBI) on a patient with no cancerous lesions can be either true negative (TN) or false positive (FP). The per-patient score will be defined as the higher score between the two breasts or, if there are multiple scored findings within a breast, the maximum score within the patient.

1. A TN test result will be defined as a negative test score on a patient with a negative reference standard. For DBT, a negative BI-RADS score will be 1 or 2; a negative test score on MBI will be a score of 1 or 2 on the 5-point assessment scale.
2. A FP test result will be defined as a positive test score on a patient with a negative reference standard (BI-RADS 0, or BI-RADS 3 or higher for DBT; 3 or higher on the MBI assessment scale).

The result of either exam on a patient with at least one cancer can be either true positive (TP) or false negative (FN).

1. A TP test result will be defined as a positive test score and correct localization of the lesion on a patient with a positive reference standard.
 - a. Correct localization will be determined by an expert radiologist reconciler as follows: A DBT or MBI finding will be deemed to correspond with a cancer (invasive or DCIS) if it is located in the same quadrant of the breast and at the same depth (anterior, middle, or posterior, if recorded on the pathology report).
 - b. Any cancer found by pathologic analysis that does not have a matching DBT or MBI finding will be considered occult (false-negative) on that modality.
 - c. Any DBT or MBI finding that does not match with a cancer on the pathology report will be considered in the analysis as a false-positive.
 - d. Two or more discrete cancerous lesions identified on pathology may be deemed to match a single DBT or MBI finding if the lesions correspond in location with a larger imaging finding (e.g., the pathology report describes several small adjacent masses in a single quadrant, where on imaging, a single larger region in that quadrant is

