described). The decision of whether several invasive foci match a single MBI finding (assuming the location matches) will be validated primarily by visual qualitative or morphologic assessment. For cases in which it is not clear qualitatively whether all foci can be accounted for by the one DBT or MBI finding, the imaging finding must be within 1 cm of the combined size of the invasive foci for them all to be included. If all invasive foci in a single quadrant cannot be accounted for by a single imaging finding, it will be assumed that the larger focus matches the imaging finding and the smaller focus or foci are occult.

- e. In patients with core biopsy-proven cancer who undergo neoadjuvant chemotherapy before definitive surgery, an imaging finding may be deemed true-positive even if surgical pathologic findings are negative, as long as the finding corresponds with the quadrant and depth of the pre-therapy positive core biopsy (validated by review of postclip films or conventional imaging of the core biopsy). Cancerous lesions found on surgical pathologic examination after chemotherapy that do not have a matching DBT or MBI finding will be considered occult on the respective modality.
2. A FN test result will be defined as either a negative test score or a positive test score but not in the correct location on a patient with a positive reference standard.

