8.6 Secondary Endpoints

- 1. To compare the rate of detection of invasive cancers between DBT alone vs. MBI alone at Year 1 screening.**

The comparison will be based on a 2-sided McNemar's test at statistical significance level alpha= 0.05.

2. To compare the screening performance metrics of sensitivity, specificity, recall rate, biopsy rate, positive predictive value and negative predictive value for DBT and MBI.

For both years of the study imaging (Year 1 and Year 2), the following secondary endpoints will be analyzed to compare performance of

- DBT alone vs. MBI alone, and
- DBT alone vs. the combination of DBT with supplemental MBI.

Sensitivity will be estimated for each modality as the proportion of women with breast cancer who have true positive test results. **Specificity** will be estimated as the proportion of women without breast cancer who have TN test results. Uncertainty in the estimate of sensitivity will be quantified through a two-sided 95% confidence interval (CI) based on the binomial distribution. If a sufficient number of radiologists interpret exams from multiple patients with breast cancer, secondary analysis may also include a 95% CI and chi-squared test adjusted for clustering of results within radiologist to allow generalization to both the population of patients and the population of radiologists.³⁶ For comparisons of DBT alone vs. the combination of DBT with supplemental MBI, a structural zero results due to the paired nature of the data and direct comparisons cannot be tested under a null hypothesis of equivalence. Analysis will alternatively focus on the conditional diagnostic odds ratio (cDOR) to quantify the added value of MBI over DBT alone.

Recall rate (defined as the proportion of patients recalled from the screening test for diagnostic workup among the total number of patients screened), and **biopsy rate** (defined as the proportion of patients in whom biopsy is generated from a particular modality among the total number of patients screened) will be estimated employing analytical strategies similar to sensitivity and specificity. McNemar's test will be used to compare rates between two modalities.

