Predictive values will be estimated for each modality based on data pooled across radiologists. PPV1 (the proportion of patients with breast cancer among patients with abnormal screening examinations), PPV3 (the proportion of breast cancers diagnosed among biopsies performed), and NPV (the proportion of patients without breast cancer among those with normal screening examinations) will be determined. The primary unit of analysis will be the patient, except for PPV3, in which the primary unit of analysis will be the biopsied lesion. The method of Moskowitz and Pepe will be used to compare relative

predictive values between the two imaging modalities.³⁷ Secondary analyses may adjust for clustering of results within radiologist.

3. To compare tumor characteristics of all cancers (invasive and noninvasive) detected on DBT and MBI, including size, nodal status, and molecular subtype.

The analysis comparing tumor characteristics will be descriptive. Size, nodal status, and molecular subtype (including estrogen and progesterone receptor status, HER-2 status, Ki-67 and Oncotype DX score as available) will be abstracted from clinical final pathology reports from all biopsies and surgeries performed. The distribution of sizes will be summarized by ordinary numeric (e.g., means, SDs, range) and graphical (e.g., histograms, density smoothers) summaries. Descriptive summaries of the lesions identified with MBI but not DBT and vice versa will also be calculated to understand the differences in performance should one be identified.

4. To assess the reduction in advanced cancer rate with incorporation of MBI screening by comparing advanced cancer rate observed at Year 2 screening relative to that at Year 1.

For the purpose of our analysis, advanced cancers are defined as cancers greater than 2 cm in maximum dimension (determined by measurements on pathology or imaging) and/or cancers that are lymph node positive, as these patients may be considered for neoadjuvant chemotherapy. To assess whether the incorporation of MBI screening reduces **advanced cancer rate**, the rate of advanced cancers detected at Year 2 screening will be compared to the rate at Year 1 screening. The rates of advanced cancers, together with their respective 95% confidence intervals, will be estimated for Year 1 and Year 2. Comparison in the rates between Year 1 and Year 2 will utilize the test of two proportions based on exact binomial distributions.

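### PPV1 carries no localisation condition, so a woman scored false negative for a modality's sensitivity can count as a success in that modality's PPV1

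*Combined protocol and SAP*

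**What the plan says.** Section 8.3 (Definitions of Screening Test Results) classifies each exam at patient level:

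- A true positive needs "a positive test score and correct localization of the lesion on a patient with a positive reference standard".
- A false negative is "either a negative test score or a positive test score but not in the correct location on a patient with a positive reference standard".
- A patient-level false positive needs a woman without cancer: "A FP test result will be defined as a positive test score on a patient with a negative reference standard".
- Item 1c deals with single findings. One that "does not match with a cancer on the pathology report will be considered in the analysis as a false-positive".

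Section 8.6, item 2, defines sensitivity as "the proportion of women with breast cancer who have true positive test results", so sensitivity inherits the localisation rule. The predictive values in the same item do not. The plan gives "PPV1 (the proportion of patients with breast cancer among patients with abnormal screening examinations", and NPV is the share without cancer among women whose exam was normal. Both are per patient; only PPV3 is per biopsied lesion. Predictive values are to be compared between modalities by the Moskowitz and Pepe method. The comparisons listed are DBT against MBI, and DBT against DBT plus MBI.

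**The concern.** Every woman has both tests. Suppose MBI finds a cancer in one place and DBT has marked something unrelated elsewhere. Section 8.3 calls that cancer occult on DBT and lowers DBT sensitivity accordingly. PPV1 as defined in section 8.6 still counts the woman as a DBT success, because she has cancer and her DBT was abnormal. DBT is thereby credited with a cancer that only MBI located.

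PPV1 is then not TP/(TP+FP) under the trial's own classification, and sensitivity and PPV1 in one report rest on different ideas of success. Nor does the plan say whether item 1c has any bearing on PPV1. Two analysts could produce different figures, and the choice could be made after the data are seen. The affected quantity is a formal between-modality comparison in a paired trial, where the misplaced credit can hide part of what the second test adds.

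**Working it through.** **Plan's own figure.** The documents state no PPV1 or NPV. The one figure that can be reproduced is the sample size in section 8.7. For a one-sided exact binomial test with p0 = 0.001, p1 = 0.004 and alpha = 0.025, N = 2631 gives a critical count of 7, exact alpha 0.0181 and power 0.9001. This agrees with the plan and does not involve PPV1.

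**Inputs.**

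- N: 2631 needed, 3006 enrolled (sections 8.7 and 8.8).
- DBT invasive detection rate, d: 4.7 per 1000 (section 8.7).
- Cancers missed by DBT and found by MBI, m: 4 per 1000 (value used for power), 5 (conservative estimate) or 5.6 (expected difference), all from section 8.7.
- DBT recall, r: not given. Assumed 7-10%, with 5-15% as a wider range.
- Assumed: an unrelated DBT mark is independent of the missed cancer, with probability r.

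**Formulas.**

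- True positives = N × d
- Mislocalised positives = N × m × r
- Abnormal exams = N × r
- PPV1 with localisation = d/r
- PPV1 as written = (d + m × r)/r = d/r + m

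Under independence the absolute rise in PPV1 equals m, whatever the recall rate. The relative rise is m × r/d.

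**DBT results (N = 3006, true positives 3006 × 0.0047 = 14.1).**

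| m per 1000 | r | Mislocalised women | PPV1 with localisation | PPV1 as written | Relative rise |
|---|---|---|---|---|---|
| 4 | 7% | 0.84 | 6.71% | 7.11% | 6.0% |
| 4 | 10% | 1.20 | 4.70% | 5.10% | 8.5% |
| 5.6 | 7% | 1.18 | 6.71% | 7.27% | 8.3% |
| 5.6 | 10% | 1.68 | 4.70% | 5.26% | 11.9% |

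At N = 2631 the percentages are the same, with 12.4 true positives and 0.74 to 1.47 mislocalised women. Over 5-15% recall the relative rise runs from 4 × 0.05/4.7 = 4.3% to 5.6 × 0.15/4.7 = 17.9%.

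**DCIS.** The 4.7 per 1000 is invasive only, while breast cancer status, and so PPV1, includes DCIS. No planning rate for DCIS is given. If DBT detects 1 to 3 per 1000 DCIS (assumed) and none is DBT-occult, the relative rise lies between 4 × 0.07/(4.7 + 3) = 3.6% and 5.6 × 0.10/(4.7 + 1) = 9.8%.

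**MBI.** Let s be the share of DBT-detected cancers that MBI also finds. MBI then misses 4.7 × (1 − s) per 1000, and by the same formula its PPV1 rises by that amount: 0.47 points at s = 0 and 0.05 points at s = 0.9. With N = 3006 and an assumed MBI recall of 6.6-10%, this is 0.1 to 1.4 women. The 6.6% is the added recall in section 1.4, the nearest figure available. The DBT rise is the larger when m > 4.7 × (1 − s). That holds for any s at m = 5 or 5.6. At m = 4 it needs s > 1 − 4/4.7 = 0.149. Cancers missed by both tests are left out here; under the same assumption they add equal points to both modalities.

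**NPV.** Take m = 5 per 1000, r = 10% and N = 3006. There are 2705.4 normal exams, of which 13.5 are in women with a missed cancer, so NPV is 99.50%. Adding the 1.5 mislocalised women to the denominator as false negatives gives 99.44%. Over 5-15% recall the difference is 0.03 to 0.09 points.

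**The case against.** The strongest reply is that PPV1 as written is a legitimate patient-level quantity: the chance that a recalled woman has cancer. It matches reports that do not localise, and it is stated openly. The affected group is also tiny. With 14 successes among 301 abnormal exams, the exact 95% interval is about 2.6% to 7.7%, and a shift of 0.4 to 0.6 points sits well inside it. All of this stands. It argues for keeping the any-cancer version in the report and against treating the matter as serious. It does not explain why sensitivity and PPV1 for the same exam should use different rules when the two modalities are being compared.

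A reader might also infer more than the documents support:

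- *That the same woman is at once FN, FP and a PPV1 success.* A patient-level false positive in section 8.3 needs a negative reference standard, so a woman with cancer cannot be one. Item 1c concerns findings.
- *That NPV is wrong in the same way.* The woman had no normal exam, so NPV leaves her out; it does not count her as a success.
- *That the distortion certainly favours DBT.* The documents give no MBI-alone recall, no overlap with DBT-detected cancers and no mislocalisation rate.
- *That the effect is larger, for example at 8 per 1000 occult on DBT.* Section 8.7 supports increments of 4, 5 and 5.6 only.

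**Conclusion.** The point holds as an inconsistency between sections 8.3 and 8.6, confined to PPV1. It is worth correcting because the remedy is easy, not because the effect is large: about 1 to 2 women against 12 to 14 DBT true positives, in one metric within a secondary endpoint.

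The direction in points (DBT raised more than MBI) is expected but conditional. It could reverse at an increment of 4 per 1000 if MBI finds fewer than about 15% of the cancers DBT detects. The sizes rest on the section 8.7 planning rates, an assumed recall rate and independence of the unrelated mark. Because recall includes the true positives themselves, setting the chance of an unrelated mark equal to recall slightly overstates the effect. Specificity, sensitivity, the primary endpoint and the sample size are not affected.

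**What to change.** In section 8.6, item 2:

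1. Define the PPV1 numerator for the modality comparisons as women with a true-positive result under section 8.3. A woman with cancer and only unmatched findings on that modality stays in the denominator as a non-success.
2. Report the any-cancer PPV1 alongside it, labelled as such.
3. State that the paired comparison of predictive values must let the numerator outcome differ by modality, since success is no longer a single disease status shared by both tests. A marginal regression on the abnormal exams clustered by woman, or a bootstrap that resamples women, would do this.

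In section 8.3, state that item 1c is lesion-level and does not reclassify the patient.

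No new data are needed, because the expert reconciler already adjudicates localisation. The costs are a slightly lower PPV1, a small adaptation of the paired method, and one extra reported figure to keep comparability with studies that do not localise.

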5.2.1 DBT Interpretation

DBT interpretation will be performed during the course of routine clinical practice by radiologists using the standard of care American College of Radiology BI-RADS lexicon.³³ For the initial screen, BI-RADS categories of 0 (incomplete), 1 (negative), or 2 (benign) will be assigned. Interpretive findings, including lesion type, size, and location will be abstracted from the clinical

DBT report by study staff. A study radiologist will review the DBT exams with BI-RADS assessment 0 and assign a lesion ID and per-lesion assessment category for each lesion identified on the clinical DBT screening report. Categories 3, 4, and 5 are considered test positive.

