8.1.3 Participants Not Meeting Reference Standard Definitions

If a participant does not meet either definition for Positive or Negative Breast Cancer Status in a given screening year, for instance a participant who has no known breast cancer diagnosis but has no information available via chart review and cannot be contacted, will be considered “lost to follow up” and assumed to not have breast cancer in the analysis. In the event of a participant’s death, the date of death and cause of death will be recorded to determine if breast cancer was diagnosed and the length of follow up.

^aThe date of histopathologic breast cancer diagnosis is defined as the date on which tissue was obtained via biopsy or surgical excision, and subsequently determined to include invasive cancer (with or without DCIS) or DCIS.

^bYear 1 screening is defined as having both Year 1 MBI and Year 1 DBT. If not performed on the same day, the date of Year 1 screening is the day Year 1 MBI is performed.

^cYear 2 screening is targeted to be performed with both MBI and DBT approximately 365 days (target range 335 – 455 days) after Year 1 screening MBI. For purposes of establishing breast cancer status of Screening Year 1, Year 2 screening may be performed with any combination of breast imaging tests, most often including MBI, DBT, or both, but may also include breast MRI, WBUS, or CEDM; testing may be performed for either screening or diagnostic indications. The date of Year 2 screening used for reference standard is the earliest of these tests performed at least 335 days after Y0 screening.

^dYear 2 screening is not conducted as part of the research study, but considered for purposes of establishing Year 2 breast cancer status as any documentation of breast imaging (MBI, DBT, MRI, WBUS, or CEDM) performed within 335 – 455 days after Year 2 screening.

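### Secondary endpoint 3 draws tumour size and nodal status only from pathology reports and has no rule for women given neoadjuvant chemotherapy, so size at detection would be understated for those who respond.

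*Combined protocol and SAP*

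**What the plan says.** Section 8.6, item 3 compares the characteristics of all cancers, invasive and noninvasive, found on DBT and MBI. Its data "will be abstracted from clinical final pathology reports from all biopsies and surgeries performed". Imaging is not named as a source, and no order of precedence is given when a woman has several reports. The item carries no test: "The analysis comparing tumor characteristics will be descriptive".

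Item 4 of the same section is broader on size: "advanced cancers are defined as cancers greater than 2 cm in maximum dimension (determined by measurements on pathology or imaging". Its second criterion is nodal, and the same sentence makes the link to treatment: "and/or cancers that are lymph node positive, as these patients may be considered for neoadjuvant chemotherapy". It does not say which measurement governs when pathology and imaging disagree, or that size and nodes must be assessed before treatment.

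Neoadjuvant chemotherapy has its own rule in one place only, section 8.3 (1e). If the finding matches the site of the pre-therapy positive core biopsy, "an imaging finding may be deemed true-positive even if surgical pathologic findings are negative". That rule concerns true-positive status and does not extend to size or nodes.

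Two other provisions bear on the point. The footnotes to section 8.1.3 fix the diagnosis date, "defined as the date on which tissue was obtained via biopsy or surgical excision", but not the stage at that date. Section 5.2.1 collects a lesion size for DBT; its sentence on the screening report begins: "Interpretive findings, including lesion type, size, and location will be abstracted from the clinical". Section 5.2.2 names no corresponding size field for MBI.

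**The concern.** Item 3 is meant to describe cancers as they were when DBT or MBI found them. For a woman who goes straight to surgery, the surgical report is a fair record of that. For a woman treated first, it records what was left after treatment. The plan recognises this in section 8.3 (1e), where it keeps a detection from being lost because surgery found nothing, but it does not carry the reasoning over to size and nodes.

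The cases affected are not a random subset. Item 4 singles out cancers over 2 cm or node positive "as these patients may be considered for neoadjuvant chemotherapy". If some of these are entered with post-treatment values, the upper end of the size distribution and possibly the node-positive count are the parts that shrink. Sections 1.4 and 1.5 rest much of the argument for MBI on node-negative detection and on uncovering large or node-positive cancers hidden on mammography, so these summaries will be read closely even though they are descriptive.

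**Working it through.** **The plan's own figure.** The only related calculation is the primary sample size in section 8.7. For an exact one-sided binomial test of 0.001 against 0.004 with N = 2631, the rejection threshold at alpha 0.025 is 7 or more. The attained level is 0.0181 and power is 0.9001, which reproduces the stated 90%. Nothing below changes it.

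**What item 3 yields for a treated woman who responds**
- Size: the sources are the core biopsy report, which does not usually give whole-tumour size, and the post-treatment surgical report. Only the second gives a whole-tumour measurement, and it may be zero.
- Nodes: a positive pre-treatment node biopsy, if one was done, is among the source reports. Nothing says it outranks a later negative surgical report, and no section requires that such a biopsy exist.
- Receptors: the core biopsy supplies them, so only precedence is missing.

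**Scale.** Section 8.7 gives a DBT invasive detection rate of 4.7 per 1000 in dense breasts and a powered increment of 4 per 1000.
- Expected Year 1 invasive cancers: (4.7 + 4)/1000 × 2631 = 22.9, about 23. With 3006 women: 8.7/1000 × 3006 = 26.2.
- Found by MBI but not DBT, a group item 3 summarises separately: 4/1000 × 2631 = 10.5.

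**Effect on mean size.** Assume a treated tumour was 3.5 cm at detection and is entered as 0.5 cm, an understatement of 3.0 cm. Neither size is in the documents, nor is the number of women treated, so the count k is left as a range.
- All Year 1 invasive cancers: shift = 3.0 × k/23. This gives 0.13 cm for k = 1, 0.26 cm for k = 2 and 0.39 cm for k = 3.
- MBI-only group: one case shifts that group's mean by 3.0/10.5 = 0.29 cm.
- Item 3 also covers DCIS. With D such cases the overall shift is 3.0 × k/(23 + D), smaller than the figures above. The documents give no value for D.
- Each woman wrongly entered as node negative lowers the node-positive share of the 23 by 1/23 = 4.3 percentage points.

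**Effect on item 4, only if post-treatment values were used there.** These are two-sided Fisher exact tests with 2631 women in each year; the counts of advanced cancers are assumed.

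| Year 1 vs Year 2 | None lost | 1 Year 1 case lost | 2 lost | 3 lost |
|---|---|---|---|---|
| 10 vs 2 | p = 0.038 | 0.065 | 0.109 | 0.179 |
| 8 vs 1 | p = 0.039 | 0.070 | 0.125 | 0.219 |
| 12 vs 4 | p = 0.076 | 0.118 | 0.179 | 0.266 |

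The first two rows start just below 0.05, so they show how sensitive the test can be and are not a forecast. Year 1 losses understate the fall from Year 1 to Year 2; Year 2 losses would overstate it.

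**The case against.** The strongest reply is that the plan is silent on precedence and does not order a wrong measurement. A reader might infer that it scores treated women on residual disease throughout, or that the largest, node-positive cancers will be recorded as small and node negative. The documents do not support either reading. Item 3 includes biopsy reports, so pre-treatment nodal and receptor results are already source data where they exist, and the word final may mean only the signed-off report on each specimen. A misrecorded cancer requires that the woman is treated before surgery, that she responds, and that no pre-treatment record is used. The plan says only that such treatment may be considered. This stands, and it narrows the nodal part. It does not rescue size, because no source named in item 3 usually holds a pre-treatment whole-tumour dimension.

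Item 4 is also largely protected on size: a tumour over 2 cm on imaging can count as advanced whatever surgery shows. That stands too. What remains exposed there is timing and precedence, chiefly for nodes.

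A reader might further infer a bias towards MBI or towards an early-detection conclusion. That is not shown. Which modality found more of the treated cancers is unknown, cancers seen on both enter both summaries, and Year 1 losses in item 4 would work against the hypothesised reduction.

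Finally, item 3 has no test or decision rule, and the size of the error rests on assumed figures. Both are true and limit the weight of the point.

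**Conclusion.** The point holds in a limited form. For women treated before surgery who respond, following item 3 as written gives a post-treatment tumour size, so the descriptive summary understates size at detection. Nodal status is at risk only where no positive pre-treatment node biopsy exists or where a later negative surgical report displaces it. The error is concentrated in the cancers that item 4 calls advanced.

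Under the assumed 3.0 cm understatement and about 23 Year 1 invasive cancers, each affected tumour moves the invasive mean by about 0.13 cm, and by less with DCIS included. The number of affected women cannot be derived from the documents, and the direction between DBT and MBI is unknown. The primary endpoint, its power and the sample size of 2631 are untouched, and detection itself is protected by section 8.3 (1e). It is a modest but non-random measurement error on a secondary endpoint, inexpensive to remove.

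**What to change.** Add to item 3: for women given systemic therapy before surgery, tumour size is the pre-treatment imaging size, and pre-treatment biopsy results for nodes and receptors take precedence over post-treatment surgical pathology where available. Flag these women and show the summaries with and without them. State in advance which imaging measurement is used. A screening DBT size cannot serve for a cancer that DBT did not show, so the rule should also draw on the diagnostic workup imaging described in section 5.3.

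In item 4, where imaging size is already allowed, add that both size and nodal status are taken before treatment.

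The cost is a few sentences in the plan and extra abstraction for the women concerned. DBT lesion size is already abstracted, but an MBI or workup size field may have to be added. There are two drawbacks. Sizes will come from two kinds of source, which the flag and the with-and-without summaries make visible. Pre-treatment nodal data may be missing for some women, and that number should be reported. The change concerns data abstraction only and has no bearing on patient care.
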